6 STUDY DESIGN

The CLOUT Registry is a prospective, multi-center, observational study of subjects with proximal lower extremity DVT treated with the ClotTriever Thrombectomy System. The Registry will collect data on demographics, comorbidities, details from the DVT diagnosis and treatment, and clinical outcomes through 2-year follow-up.

Up to 500 subjects with proximal lower extremity DVT will be enrolled at up to 50 Registry sites. All subjects who sign consent and are treated with the ClotTriever System will comprise the Full Analysis dataset.

The Primary Analysis datasets will be derived from the 500 subject Full Analysis dataset. Hypothesis testing will be performed on this dataset; the safety endpoint testing will be performed on the Primary Analysis Safety cohort and the effectiveness endpoint testing will be performed on the Primary Analysis Effectiveness Cohort.

- The Primary Analysis Safety cohort will include the first 91 subjects that enroll with a clinical presentation analogous to that used for the literature-derived performance goal (i.e., unilateral acute or subacute DVT of less or equal to 6 weeks' duration). These first 91 subjects will not have been not treated with thrombolytic or percutaneous mechanical thrombectomy within the prior 3 months.
- From these same 91 subjects, the Primary Analysis Effectiveness cohort will be the subset of subjects who undergo treatment with the ClotTriever System in venous segments with Core Laboratory determined intraluminal thrombus.

Once the Primary Analysis cohort is fully accrued, subjects meeting these criteria will continue to be enrolled and will be evaluated as part of the Full Analysis dataset.

The primary safety endpoint will be assessed when the 30-day follow-up data on the 91-subject Primary Analysis cohort is complete (see Section 10.4), allowing evaluation of both the primary safety and effectiveness endpoints. The remainder of the subjects will be enrolled to obtain additional safety and effectiveness data and to allow subset analyses of various pre-determined subgroups. Subjects in both arms will be followed for 2 years after the index procedure.

6.1 STUDY POPULATIONS

The study will consist of up to 500 subjects, i.e., the Full Analysis dataset, who meet the eligibility criteria and are appropriate candidates for treatment with the ClotTriever Thrombectomy System. The Primary Analysis dataset is a subset of subjects with unilateral acute or subacute DVT of less or equal to 6 weeks' duration, without recent (≤3 months) venous intervention. The first 91 subjects enrolled who meet these criteria will complete the Primary Analysis dataset. Enrollment of this type of subject will continue once the Primary Analysis cohort is fully accrued, i.e., past the 91 subjects needed for the primary endpoint analyses. These additional subjects will be included in the Full Analysis dataset.

6.2 Informed Consent

Written, study-specific Informed Consent will be obtained from each subject prior to the subject's deidentified medical record or personal health information (PHI) being shared with any study representative. The Investigator will keep the original Informed Consent Form and a copy will be given to the subject. The subjects will be informed that they are free to refuse entry into the study and free to withdraw from the study at any time without prejudice to future treatment. See Section 7.2 for additional information regarding the timing of consent and the point of enrollment.

6.3 Point of Enrollment

The ClotTriever System is not being used in an investigational manner and the patient will be treated with the device in the same manner regardless of whether the patient enrolls in the study. Therefore, the patient's consent for treatment is covered under the institution's internal procedures. To participate in the study, the patient must consent to share his/her deidentified personal health information (PHI) with the study sponsor. This allows sites to treat patients prospectively and consent patients after treatment. This can be helpful for sites when the research staff is unavailable to consent the patient prior to the index procedure (i.e., after hours, weekends, holidays). This practice is allowed provided there is no institutional prohibition against post-procedure consent.

Pre-procedure consents are the preferred consenting method and should be obtained within 7 days of the scheduled index procedure as part of the baseline work-up. When post-procedure consents are obtained, the consent must be obtained after the patient gains full capacity after anesthesia and within 7 days of the index procedure.

If the ClotTriever System does not enter the patient's vasculature, the patient is considered a screen failure and as such, his/her data is not to be entered into the database. A patient is considered enrolled when 1) the device enters the patient and 2) the patient consents to the study. The timing of the two events, index procedure and consent, are interchangeable.

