5 OUTCOME VARIABLES

5.1 PRIMARY SAFETY ENDPOINT DEFINITION

The primary safety endpoint is the rate of Major Adverse Events (MAE). MAEs are defined as a composite endpoint triggered when any of four categories of events through 30 days after the index procedure, as observed in the Primary Analysis Safety Cohort:

- All-cause mortality
- Major bleeding
- New symptomatic PE documented by CTPA
- Rethrombosis of a target venous segment (TVS)

The components of the composite MAE endpoint will be assessed by the independent Medical Monitor.

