13 ETHICS

13.1 INFORMED CONSENT

Written informed consent will be obtained from each subject prior to the subject's medical record or personal health information being shared with any study representative. The subject's willingness to participate in the study will be documented in writing in a study-specific Informed Consent Form, which will be signed and dated by the subject or Legally Authorized Representative. The Investigator will keep the original consent form and a copy will be given to the subject. It will be explained to the subjects that they are free to refuse entry into the study and free to withdraw from the study at any time without prejudice to future treatment. Subjects will be consented for two years or for the duration of the subject's participation in the study.

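### Post-procedure consent under Protocol 6.3 permits survivor and outcome-aware selection, of unknown size, into both primary analyses

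*Protocol*

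**What the plan says.** Protocol 6.3 separates treatment from joining the study: "This allows sites to treat patients prospectively and consent patients after treatment". It defines entry to the study by two events: "A patient is considered enrolled when 1) the device enters the patient and 2) the patient consents to the study". It adds: "The timing of the two events, index procedure and consent, are interchangeable".

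Consent before the procedure is favored but not required: "Pre-procedure consents are the preferred consenting method and should be obtained" within 7 days of the scheduled procedure. The later route is offered for times when research staff are absent, and only where the institution does not forbid it. On that route, "When post-procedure consents are obtained, the consent must be obtained" once the patient has fully recovered capacity after anesthesia, and no later than 7 days after the procedure.

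On who may sign, Protocol 6.4.3 requires that the patient be both willing and able to consent. Protocol 13.1 instead has the form "signed and dated by the subject or Legally Authorized Representative".

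The primary safety set is built from enrolled subjects: "The Primary Analysis Safety cohort will include the first 91 subjects that enroll with a clinical presentation analogous" to that behind the literature-derived goal (Protocol 6; SAP 2 and 3.2 match). The MAE period in Protocol 5.1 runs for 30 days from the index procedure, not from consent, and its first listed component is "All-cause mortality".

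Neither document has a consecutive-enrollment rule, a log of treated patients who were not enrolled, or an analysis by consent timing. SAP section 4 deals with incomplete dates and with missing effectiveness data in enrolled subjects only.

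**The concern.** For anyone on the later route, the endpoint clock is already running before the patient can belong to the study. Two kinds of selection follow.

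- **Forced loss.** A patient without prior consent who dies before signing is in neither the numerator nor the denominator. Loss of capacity may have the same effect, depending on which consent section governs.
- **Outcome-aware approach.** Technical Success is fixed by the venogram taken after the device and before any adjunctive therapy. By the time a patient is approached for late consent, the operator has seen that venogram, and early bleeding or rethrombosis may also be known. Nothing obliges the site to approach every treated patient.

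This is a single-arm study tested against fixed goals (Protocol 10.1), so there is no concurrent control in which the selection could cancel. Success requires both endpoints to meet their goals (Protocol 10.4). At stake is the false-success rate of each test.

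**Working it through.** **1. The plan's own figures.** Inputs from Protocol 10.8 and SAP 5.1: goal 34%, anticipated MAE rate 20%, one-sided exact binomial test at 0.025. The test passes at the largest c with P(X ≤ c | n, 0.34) ≤ 0.025, and power is P(X ≤ c | n, 0.20).

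- n = 86: c = 20, actual alpha 2.1%, power 81.5% (stated 82%). 86/0.95 = 90.5, rounded up to 91. Both reproduce.
- n = 91: c = 21, actual alpha 1.6%, power 80.8%.

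The sample size figures are sound and do not depend on this point.

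**2. Direction of forced loss.** Let p be the true MAE rate and g the share of treated, otherwise eligible patients who have an MAE and are lost before consent. The observed rate is (p − g)/(1 − g), which is below p for any g > 0 when p < 1. Forced loss can only lower the observed rate.

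**3. Size for safety.** The documents do not give q, the share of the cohort consented afterwards, or e, the share of MAE patients on that route who never enroll. Both are assumed. The range for e covers death, incapacity and non-approach together.

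Observed rate on the later route = 0.34(1 − e)/(1 − 0.34e). Cohort rate = (1 − q)(0.34) + q × that value. Chance of passing = P(X ≤ 21 | 91, cohort rate).

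Example with q = 0.5 and e = 0.10: 0.306/0.966 = 31.7%; the cohort rate is (34.0 + 31.7)/2 = 32.8%; the chance of passing is 2.8%.

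| Consented afterwards (q) | e = 5% | e = 10% | e = 20% | e = 30% |
|---|---|---|---|---|
| 10% | 1.7% | 1.8% | 2.0% | 2.3% |
| 25% | 1.9% | 2.1% | 2.9% | 3.8% |
| 50% | 2.1% | 2.8% | 4.8% | 8.2% |
| 100% | 2.8% | 4.7% | 12.0% | 27.1% |

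With no selection the figure is 1.6%; the nominal level is 2.5%.

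**4. Threshold in g.** Using the formula in step 2, the chance of a false pass exceeds 2.5% once g is about 0.6% at n = 86, since (0.34 − 0.006)/0.994 = 33.6%, or about 1.4% at n = 91.

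**5. Fragility of a borderline pass.** Exact upper limits at n = 91, adding lost MAE cases back to numerator and denominator:

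- 21/91: 33.1%, passes.
- 22/92: 33.9%, passes.
- 23/93: 34.8%, fails.

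At n = 86, 20 events pass (upper limit 33.6%), and one added case (21/87, 34.5%) fails.

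**6. Technical Success.** With 88 subjects and a goal of 30%, the test passes at 36 or more successes (actual alpha 1.9%). If a share e of failures on the later route is not approached, the observed success rate there is 0.30/(1 − 0.70e). With q = 0.5 and e = 10%, 20% or 30%, the chance of passing at a true 30% is 3.3%, 5.9% or 10.5%. Here e is purely a non-approach rate and is entirely assumed.

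**The case against.** The strongest reply is that the later route is an exception whose effect may be negligible.

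- Consent beforehand is the preferred method, and anyone who signs beforehand stays in the count whatever happens next. This stands. The loss applies only to patients without prior consent.
- Much of the composite is not forced out. A patient with a nonfatal bleed or PE who keeps capacity can still sign within 7 days. Rethrombosis needs imaging of an occlusion (Protocol 15), and the first scheduled follow-up duplex is at 14 to 45 days, after the consent window has closed. The row that SAP Table 3 adds for rethrombosis supplies 75 of its 198 events. This stands against applying a large loss fraction to all MAEs.
- The upper assumptions are high. Losing 10–30% of MAE patients at a 34% rate means that 0.34 × 10% = 3.4% to 0.34 × 30% = 10.2% of all later-route patients have an MAE and go unenrolled. Protocol 1.2 gives 5% case fatality in hospitalized DVT, and life expectancy under 1 year is an exclusion. With 10% consented afterwards, even a 30% loss leaves the chance of passing at 2.3%, below nominal.
- The core laboratory reads the venograms independently. This protects the measurement, not the choice of whom to enroll. Nothing in the documents, however, shows that sites choose by result.

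A reader might infer that any patient who loses capacity is shut out. The documents do not settle that. The 6.3 wording can be read as a recovery-from-sedation rule, and 13.1 lets a representative sign. Only death before signing is certain to exclude. A reader might also infer that the literature goals carry no matching selection, but SAP 5.2 does not say how the source studies enrolled their patients.

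**Conclusion.** The mechanism holds: Protocol 6.3 permits survivor and outcome-aware selection, no safeguard addresses it, and the forced part can only favor success on safety. Its size is unknown, because the share of late consents and the early-loss rate are both absent from the documents.

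Over the assumed ranges (10–100% consented afterwards, 5–30% of their MAE patients lost), the chance that a device with a true MAE rate of 34% passes at n = 91 lies between 1.7% and 27.1%, against 1.6% without selection. Where the later route is rare it stays under 2.5%. A result near the boundary could nevertheless turn on one or two unenrolled cases.

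A reader might conclude that the MAE rate is biased low by design, or that the study will succeed through selection alone. The documents do not support that. They show that the bias is possible, not that it occurs or that it is large.

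**What to change.** 1. Record the timing of consent relative to device entry for every subject.
2. In SAP 5.3 and 5.4, prespecify a repeat of both primary analyses in subjects consented before the procedure. Report each as an estimate with its interval, not as a pass/fail test: if half the cohort qualifies, safety power is about 44% at 45 subjects and 56% at 46.
3. Have sites report, where the IRB allows, an aggregate de-identified count of device-treated, otherwise eligible patients who were not enrolled, including deaths within 7 days. IRB agreement matters because Protocol 6.2 bars sharing a patient's record before consent.
4. Add a tipping-point analysis to SAP 5.3 that counts those deaths as MAEs.
5. Reconcile Protocol 6.3, 6.4.3 and 13.1 on who may consent.

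The cost is some wording, one count per site and a wider interval in the subset. Total enrollment does not change. If the first 91 are not yet fixed, restricting them to pre-procedure consents would remove this selection, probably at the price of a later primary readout. That is an option to weigh, not a required change.

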| experience, which were furnished to me by | information on the device relating to past non-clinical and clinical the Sponsor, to all physicians and other study personnel responsible to scuss this material with them to ensure that they are fully informed e study. |
| | nation (e.g., source documents and informed consent forms) and all ly, in accordance with local and national regulations. |
| | |
| | |
| | |
| Investigator's Signature | Date |
| | |
| | |
| | |
| | |
| | |

SYNOPSIS

| Protocol Number | 18-001 |
|--|---|
| Study Title | ClotTriever Outcomes (CLOUT) Registry |
| Study Device | ClotTriever® Thrombectomy System |
| Regulatory Status | The ClotTriever Thrombectomy System was cleared in the US under 510(k) number K163549, February 16, 2017. The device is indicated for the non-surgical removal of soft thrombi and emboli from peripheral blood vessels. |
| Sponsor | Inari Medical [name] |
| Primary Study Objective | The primary objective of this study is to evaluate real world patient outcomes after treatment of acute, subacute, and chronic proximal lower extremity deep venous thrombosis (DVT) with the ClotTriever Thrombectomy System. |
| Study Population | The Full Analysis dataset comprises up to 500 subjects with proximal lower extremity DVT. |
| | The Primary Analysis datasets are subsets of the Full Analysis dataset, comprising 91 subjects with unilateral acute or subacute DVT of less than or equal to 6 weeks' duration. |
| | Primary Safety Cohort are subjects in the Primary Analysis dataset who were not treated with thrombolytic or percutaneous mechanical thrombectomy within the prior 3 months. |
| | Primary Effectiveness Cohort are subjects in the Primary Analysis dataset with core laboratory-documented intraluminal thrombus at baseline who have at least one target venous segment (TVS) treated with the study device. |
| Number of Sites | The study will be conducted at up to 50 sites. |
| Study Design | The CLOUT Registry is a prospective, multi-center, observational study of subjects with proximal lower extremity DVT treated with the ClotTriever Thrombectomy System. The Registry will collect data on demographics, comorbidities, details from the DVT diagnosis and treatment, and clinical outcomes through 2-year follow-up. |
| Primary Endpoints (Primary Analysis Cohorts) | Primary Safety Endpoint: Composite of Major Adverse Events (MAEs) through 30 days defined as one or more of the following: |

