7.3 INDEX PROCEDURE

Thrombectomy using the ClotTriever System is considered the index procedure and the treatment phase of the study. The procedure is conducted under fluoroscopic/angiographic guidance. Refer to the Instructions for Use (IFU) for techniques and methods for device deployment.

Anticoagulation therapy to ensure an activated clotting time of 250 – 300 seconds is recommended.

Subjects who require conversion to open surgery due to treatment failure with the device will be followed for safety through 30 days, or until any treatment related adverse events resolve, which ever is later.

The following data are to be recorded on the subject's Procedure CRF.

- Length of procedure (from ClotTriever sheath access to last removal of sheath)
- Number of ClotTriever passes
- Number of ClotTriever devices used, with lot numbers
- Largest sheath size used
- Pre- and post-procedure venogram findings
- Pre- and post-procedure IVUS measurements
- Concurrent use of balloon angioplasty and/or stenting and/or placement of IVC Filter
- Adjunctive therapy (thrombolysis and/or additional thrombectomy).
- Anticoagulant used and amount

Venogram runs/cines must be, and IVUS runs should be, acquired pre-ClotTriever and post-ClotTriever^d. If adjunctive therapy is used, a third venogram and IVUS run post-therapy will be acquired. All procedural venograms cines and IVUS images will be de-identified, labeled appropriately, uploaded and sent to the Core Laboratory.

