7.4 TARGET VESSEL SEGMENT (TVS) ASSIGNMENT

The target vessel segment (TVS) is thrombus-containing venous segments, specified by the operator, that were treated with the study device at the index procedure. These segments may include the popliteal vein, caudal femoral vein, cranial femoral vein, profunda/deep femoral vein, common

femoral vein, external iliac vein, internal iliac vein, common iliac vein, or the inferior vena cava. The TVS does not include segments that were not intentionally treated but were instead passed through to remove the device from the leg.

All vessels treated in one leg/side are recorded under one TVS. There are three possible TVS designations:

- For unilateral treatment: TVS 1 = Leg 1 and can be any or all segments from the IVC to the popliteal
- For bilateral treatment only: TVS 2 = Leg 2 and will not include the IVC (if the IVC was treated, record it as part of TVS 1)
- For IVC treatment only: Neither leg was treated, and the treatment was IVC only (designate as TVS 1)

d Ballooning and/or stenting and/or IVC placement during the procedure is routine and not considered adjunctive therapy. Adjunctive therapy includes thrombolysis and additional thrombectomy

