7.9 WITHDRAWALS AND LOST TO FOLLOW-UP

Participation is completely voluntary, and each subject is free to withdraw from the study at any time. An investigator also has the right to withdraw the subject from the study in the event of reasons concerning the health or well-being of the subject, or in the case of lack of cooperation. Should a subject decide to withdraw for any reason, or should the investigator decide to withdraw the subject, all efforts will be made to complete and report the observations up to the time of withdrawal as thoroughly as possible. A complete final evaluation at the time of the subject's withdrawal must be made and an explanation given as to why the subject is withdrawing or being withdrawn from the study.

The reason for and date of withdrawal must be recorded on the subject's End of Study/Study Exit CRF. If the reason for the withdrawal is a device-related or procedure related AE, the event must be reported to the Sponsor and recorded in the CRF.

If the procedure is aborted, the subject does not need to complete the follow-up assessments, unless the subject is converted to surgical repair. Subjects who require conversion to open surgery due to treatment failure with the device will be followed for safety through 30 days, or until any treatment related adverse events resolve, which ever is later. The subject's enrollment roster position may not be made available to other subjects (i.e., the subject will not be replaced).

All efforts will be made to return subjects for all the follow-up visits. Due diligence in reaching the subject must be made by two documented telephone contact attempts, emails, or regular postal mail letters. After the above attempts are made, if no response is obtained, the final evaluation of the subject will be the last visit at which study-related procedures were performed. The End of Study/Study Exit CRF page will be completed, and communication attempts will be documented.

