10.3 PRIMARY EFFECTIVENESS ENDPOINT ANALYSIS

The primary effectiveness endpoint is Technical Success, defined by complete or near complete thrombus removal. Thrombus removal is determined by the Marder score at the index procedure, measured after use of the study device but prior to the use of adjunctive devices. Effectiveness will be assessed in the Primary Analysis Effectiveness Cohort^f and will be compared to a performance goal with the following null and alternative hypotheses:

 H_0 : $P_E \le PG_E$ versus H_A : $P_E > PG_E$

where P_E is the proportion of subjects with Technical Success, as defined complete or near complete removal of thrombus with the study device, defined by venographically-determined reduction of \geq 75% in the Marder score in

f This dataset was designed to exclude those subjects treated who underwent venous thrombectomy for lesions that were non-thrombotic in nature. For instance, those with non-thrombotic May-Thurner lesions that have externa compression or scar but who do not have demonstrable intraluminal thrombus. These subjects will remain in the Primary Safety Cohort and will be assessed for safety endpoints but will not be assessed for the effectiveness endpoints.

the TVSs. The effectiveness performance goal, PG_E, is Technical Success defined in the same manner, derived from the published literature.

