10.8 SAMPLE SIZE

The performance goal of 34% has been established for the primary safety endpoint, based on a one-sided 97.5% exact binomial test. The 30-day MAE rate is anticipated to be approximately 20%. Under this assumption, the required sample size to achieve a level of 82% power is 86 subjects (**Table 2**). Assuming 5% attrition over 30 days, enrollment of 91 subjects is necessary for the Primary Analytic Dataset.

Table 2. Sample Size - Primary Safety Endpoint

| Measure | |
|------------------------------|-------------------------------|
| Performance goal | 34% |
| Anticipated freedom from MAE | 20% |
| Significance level | .025 |
| Statistical test | One-sided exact binomial test |
| Desired power level | 82% |

| Required sample size prior to 5% 30-day attrition rate | 86 |
|--|----|
| Required sample size after attrition adjustment | 91 |

A performance goal of 30% has been established for the primary effectiveness endpoint. Anticipating an actual Technical Success rate of approximately 50%, and based upon a one-sided 97.5% exact binominal test, the required sample size to achieve a level of 97% power is 85 subjects (**Table 3**). Since the primary effectiveness endpoint is determined at the time of the index procedure, no attrition has been considered for lost to follow-up or other censoring events. However, the effectiveness endpoint is evaluated in the Primary Analytic Effectiveness cohort, and it is assumed that 3% of enrolled subjects will be treated for DVT in the absence of core laboratory-assessed visible thrombus in the TVS. Assuming a 3% attrition rate for subjects without thrombus, enrollment of 88 subjects will be necessary.

Table 3. Sample Size - Primary Effectiveness Endpoint

| Measure | |
|--|-------------------------------|
| Performance goal | 30% |
| Anticipated technical success rate | 50% |
| Significance level | .025 |
| Statistical test | One-sided exact binomial test |
| Desired power level | 97% |
| Required sample size prior to 3% attrition for subjects without thrombus | 85 |
| Required sample size after attrition adjustment | 88 |

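### Subjects with thrombus but no segment treated leave the Technical Success denominator, and missing 30-day MAE status has no sensitivity analysis

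*Protocol*

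**What the plan says.** **Entry and denominators.** Protocol 6.3 defines enrolment by two events: "A patient is considered enrolled when 1) the device enters the patient and 2) the patient consents to the study". Protocol 6 and SAP 2 describe the parent dataset differently: "All subjects who sign consent and are treated with the ClotTriever System will comprise the Full Analysis dataset". Within the 91 Primary Analysis subjects, the Synopsis restricts the Effectiveness cohort to those with core-laboratory thrombus "who have at least one target venous segment (TVS) treated with the study device"; Protocol 6 and SAP 2 likewise require treatment in thrombus-bearing segments. Protocol 7.4 and 15 define a target venous segment (TVS) as one "specified by the operator, that were treated with the study device at the index procedure", so with no treatment there is no TVS.

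**Reason given.** Protocol 10.3, footnote f (SAP 5.4, footnote a) explains the restriction: "This dataset was designed to exclude those subjects treated who underwent venous thrombectomy for lesions that were non-thrombotic in nature". The sample size allows for nothing else: "it is assumed that 3% of enrolled subjects will be treated for DVT in the absence of core laboratory-assessed visible thrombus in the TVS" (Protocol 10.8, SAP 5.1).

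**Missing safety outcomes.** Protocol 7.9 states: "If the procedure is aborted, the subject does not need to complete the follow-up assessments, unless the subject is converted to surgical repair". Protocol 10.5 says that the SAP will specify imputation methods and sensitivity analyses. SAP 4 sets a general rule of no imputation, then an exception for effectiveness data: random draws from measured subjects, checked by a tipping-point analysis. SAP 5.3, the safety analysis, has no missing-data rule. Protocol 10.8 and SAP 5.1 size the safety test on 86 evaluable subjects of 91 enrolled.

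**The concern.** Study success (Protocol 10.4) needs two single-arm rates to beat fixed goals of 34% and 30%. No control arm offsets a shift in either denominator.

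For effectiveness, a thrombus-bearing case in which the device achieved nothing is a poor result for the device, yet the cohort rule removes it. The exclusion therefore reaches further than its stated purpose, and in the favourable direction. If such a subject were instead read as a cohort member with missing data, SAP 4 would impute the result from measured subjects. On neither reading is the case a failure.

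For safety, the plan expects about five subjects without 30-day status. Aborted, unconverted cases are excused from follow-up assessments and could add to that number, and they need not resemble completed cases. A pass close to the boundary could rest on these unknown outcomes, and no planned analysis would show it.

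**Working it through.** All limits are exact (Clopper-Pearson), one-sided 97.5%. I take the safety criterion as an upper limit of the MAE proportion below 34%, which is what the hypotheses in SAP 5.3 require.

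**Inputs** (Protocol 10.8, SAP 5.1): safety goal 34%, anticipated MAE 20%, 86 of 91 evaluable; effectiveness goal 30%, anticipated success 50%, 85 evaluable of 88.

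**The plan's own figures**
- Safety, n = 86: pass at ≤20 events, since P(X ≤ 20 | 0.34) = 0.0209. Power P(X ≤ 20 | 0.20) = 81.5% (stated 82%). 86/0.95 gives 91.
- Effectiveness, n = 85: pass at ≥35; power P(X ≥ 35 | 0.50) = 95.9% (stated 97%). 85/0.97 gives 88. At n = 88: pass at ≥36, power 96.5%.

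**Effectiveness.** Let k of 88 thrombus subjects have no segment treated. The documents give no frequency, so k is an assumption. Excluding them leaves n = 88 − k.
- *False success.* If the true rate over all 88 is 30% and the k are all failures, the rate among those analysed is p = 0.30 × 88/n. False success is P(X ≥ r | n, p), where r is the pass count for n.
- *Pass probability.* At a true 50% among those treated, compare P(X ≥ r | n, 0.50), excluded, with P(X ≥ 36 | n, 0.50), counted as failures in 88.

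| k | n | r | p | false success | pass, excluded | pass, as failures |
|---|---|---|---|---|---|---|
| 0 | 88 | 36 | 0.300 | 1.9% | 96.5% | 96.5% |
| 1 | 87 | 36 | 0.303 | 1.9% | 95.7% | 95.7% |
| 2 | 86 | 35 | 0.307 | 3.1% | 96.7% | 94.7% |
| 5 | 83 | 34 | 0.318 | 4.9% | 96.1% | 90.6% |

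At the boundary, 35/86 passes (lower limit 30.2%), but the same 35 successes in 88 fail (29.5%).

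**Safety.** With five missing, complete-case analysis passes at up to 20/86 (upper limit 33.6%; 21/86 gives 34.9%). Over all 91, 21 events pass (33.1%) and 22 fail (34.3%). So x observed events passing complete-case are reversed if the five missing contain at least 22 − x MAEs.

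The chance that a complete-case pass is reversed is the sum over x = 17 to 20 of P(X = x | 86, 0.20) × P(Y ≥ 22 − x | 5, q), where q is the MAE rate among the missing.

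| x | P(X = x) | MAEs needed among 5 | q = 20% | q = 40% | q = 100% |
|---|---|---|---|---|---|
| 17 | 0.1073 | 5 | 0.0003 | 0.0102 | 1 |
| 18 | 0.1028 | 4 | 0.0067 | 0.0870 | 1 |
| 19 | 0.0920 | 3 | 0.0579 | 0.3174 | 1 |
| 20 | 0.0771 | 2 | 0.2627 | 0.6630 | 1 |
| **Sum of products** | | | **2.6%** | **9.0%** | **38%** |

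With 16 or fewer observed events, no pattern among the five can reverse the pass.

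**The case against.** **Technical Success needs a treated segment.** Protocol 15 defines it as the fall in Marder score over treated segments divided by their baseline score. With nothing treated there is no such ratio, and a treated-subject denominator is a recognisable choice. This stands as an explanation of how the rule arose. It does not justify dropping thrombus-bearing cases, because the footnotes give only non-thrombotic lesions as the reason, and failure can be assigned by rule without a ratio.

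**Such subjects are not lost from the 91.** A reader might infer from the word "treated" in Protocol 6 and SAP 2 that they fall outside the Primary Analysis dataset. The documents largely settle this the other way: Protocol 6.1 and SAP 3.2 take the first 91 enrolled, Protocol 6.3 defines enrolment by device entry and consent, and Protocol 7.9 says that an aborted case is not replaced. What remains is a wording mismatch.

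**The MAE rule is not absent.** A reader might infer that missing MAE status has no handling at all. The no-imputation rule in SAP 4 and the 86-of-91 sizing amount to a complete-case plan. Only the sensitivity analysis is missing.

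**Events in aborted cases are not ignored.** Protocol 7.9 waives follow-up assessments, but Protocol 9.2 still makes deaths, bleeding, new symptomatic PE and rethrombosis reportable. Without a treated segment, TVS rethrombosis cannot arise either. This stands and narrows the safety gap, but waiving the visits still makes 30-day status less certain. Nor do the documents say that aborted cases make up the 5% attrition, so the five-missing calculation describes attrition in general.

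**Conclusion.** The concern holds, at modest size, on both endpoints.

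For effectiveness, the cohort rule excludes more than its rationale supports, in the device's favour. One such case changes nothing. Two to five raise false success from 1.9% to between 3.1% and 4.9% if all are failures. At a true 50% among those treated, the pass probability differs by 2.0 points at k = 2 (96.7% against 94.7%) and 5.5 points at k = 5 (96.1% against 90.6%). The values of k are assumed.

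For safety, SAP 4 does not deliver for MAE the sensitivity analyses that Protocol 10.5 announces. It would be tempting to say that the missing outcomes have a 38% chance of deciding the verdict. That figure needs all five missing subjects to have had an MAE, and nothing in the documents suggests so. At a 20% rate among the missing the chance is 2.6%, at 40% it is 9.0%. These figures assume five missing, a 20% rate among those observed, and independence between subjects. The sample size and the primary tests are not put in doubt.

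**What to change.** - Define the Effectiveness cohort as device-entered Primary Analysis subjects with core-laboratory thrombus on the pre-device venogram. Protocol 7.3 already requires that image: "Venogram runs/cines must be, and IVUS runs should be, acquired pre-ClotTriever". Count no segment treated as Technical Success failure, neither excluded nor imputed.
- Reconcile the description of the Full Analysis dataset in Protocol 6 and SAP 2 with enrolment in Protocol 6.3, leaving the definition of a treated TVS unchanged.
- Ascertain 30-day MAE status for aborted cases and keep them in the safety denominator.
- State complete-case as the primary MAE analysis in SAP 5.3, and add a worst-case and a tipping-point analysis over the missing MAE outcomes, matching the method that SAP 4 already uses for effectiveness.

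The cost is a short protocol and SAP amendment with IRB approval (Protocol 11.2), 30-day contact for a few aborted cases, and possibly slightly less favourable reported rates. Accrual does not change, and the complete-case safety test keeps its 81.5% power at 86 evaluable subjects.
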